8.10 Reporting Requirements to the Human Research Protection Office (HRPO)

The HRPO requires approval of protocol amendments, acknowledgement or acceptance of continuing review documents, reporting of protocol deviations, serious adverse events, and unanticipated problems. The following is a synopsis of what must be reported.

- Major amendments and amendments that increase risk to subjects must be pre-approved.
- All other amendments must be submitted for acceptance with the continuing review report.
- Unanticipated problems involving risks to subjects or others, serious adverse events related to participation, and deaths related to participation must be promptly reported.
- Suspensions, voluntary/involuntary clinical holds, or any terminations of the research must be promptly reported to the HRPO.
- Deviations that affect the safety or right of subjects or the integrity of the study must be promptly reported; exceptions (from approved inclusion/exclusion criteria or stopping criteria) must be pre-approved.
- Continuing Review reports and IRB approval documentation must be submitted as soon as the documentation is available. All amendments that occurred during the reporting period must be submitted at this time.
- The final study report and any supporting documents must be submitted to the HRPO as soon as all documents become available.
- The knowledge of any pending compliance inspection/visit by the FDA, OHRP, or other government agency concerning the DOD supported research, the issuance of Inspection Reports, FDA Form 483, warning letters, or actions taken by any Regulatory Agencies including legal or medial actions and any instances of serious or continuing noncompliance with the regulations or requirements must be reported immediately to the HRPO.
- Accurate and complete study records must be maintained and made available to representatives of

the USAMRMC as a part of their responsibility to protect human subjects in research.

8.11 Reporting to FDA

Reporting to FDA will be accomplished within the regulatory time frame by the Regulatory Representative. For each adverse event observed, the Principal Investigator must decide whether it meets the definition of a “serious” adverse event. The regulatory definition of a serious adverse event is an event that is fatal or life threatening, results in persistent or significant disability, requires intervention to prevent permanent impairment/damage, or an event that results in congenital anomaly, hospital admission or prolongation of hospitalization. These will be reported within 24 hours by phone and by fax to the Regulatory Representative and submitted to FDA within the regulatory timeframes, and followed up in a timely manner. Regulatory Representative contact information is provided below.

[name]
[contact]
Email: [contact]
[contact]

The Regulatory Representative will confer with the sponsor’s medical monitor prior to submission. The sponsor has not given up the SAE reporting responsibility and will remain responsible for such.

On days of pure tone air conduction threshold testing, data will be stored for each ear of every subject in the computerized audiometer and will be exported to a centralized Microsoft Access database. These data will also be imported into an Excel spreadsheet for storage and input into a statistical package for offline data analysis. The identifiers in the computer databases will consist solely of the subject identification number (PIN).

10.0 STATISTICAL CONSIDERATIONS

10.1 Sample Size Justification

Based upon the results of the 2004 study at the Marine Corps Recruit Depot (MCRD), it is estimated that the rate of significant threshold shift (STS) will be approximately 38% for the control (placebo) group. A power analysis incorporating a 95% confidence level ($\alpha = 0.05$), 80% power, a 1:1 ratio (placebo to D-methionine), and a detectable difference in threshold shift rates of 30% yields a required sample size of 252 subjects for each of the two arms (placebo and D-methionine) of the study. Thus a total of 504 subjects need to complete the study. Assuming an attrition rate of 20% in each arm over the course of the study, a total of 600 subjects will need to be enrolled.

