4.8 Subject Replacement

If a subject receives any part of the investigation treatment, and must discontinue treatment for any reason, they will not be replaced.

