10.2 Primary Efficacy Analysis

Two groups are planned in the randomized prospective design: the D-met and the placebo groups. The primary objectives, and their associated analyses, for this study are as follows:

1. To determine if there is a significant difference between the D-methionine and placebo treated groups in the average severity of documented side effects where severity is defined as the frequency of side effect multiplied by the intensity of the side effect. Repeated measures analysis of variance (ANOVA) will be utilized to determine significance.
2. To determine if there is a significantly reduced change in threshold hearing in each ear, adjusting for handedness, for the D-methionine group as compared to the placebo group at the tested audiometric frequencies. The tested audiometric frequencies will be 0.5, 1, 2, 3, 4, 6 and 8 kHz. Multi-way (2 groups x 7 frequencies) analysis of variance (ANOVA) with interaction effects and correction for multiple comparisons (Newman-Keuls) will be utilized to determine significance. Determination for early detection will be according to the American Speech-Language Hearing Association (ASHA, 1994) criteria of: 1) greater than or equal to a 20 dB change at any frequency, 2) greater than or equal to a 10 dB change at any 2 adjacent frequencies, or 3) loss of response at 3 consecutive frequencies where responses were obtained at baseline. To be considered significant ototoxicity, these changes must replicate within 24 hours (may be immediate) with no indication of middle ear abnormality. Subjects serve as their own controls for audiometric change, which is computed relative to baseline measures.
3. To determine if there is a significantly lower rate of STS (in either ear) for the D-methionine group as compared to the placebo group where STS is defined according to DOEHRSHC criteria as an increase of 10 dB or greater change (decrease in hearing) for the average of 2, 3 AND 4 kHz in

either ear. A significant negative STS (improved hearing) is defined as a decrease of 10 dB or greater change for the average of 2, 3 AND 4 kHz in either ear. An early warning shift STS (decrease in hearing) is defined as a 15 dB or greater change at 1, 2, 3 OR 4 kHz in either ear. Fisher's exact test will be utilized to determine statistical significance.

Secondary objective of the study is as follows:

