1. To determine if there is a significant difference in reported level of tinnitus between the D-methionine and the placebo groups where the level (loudness) of tinnitus will be scored on an eleven point scale with a value of 0 associated with very quiet and a value of 10 associated with very loud and on an eleven point scale where the degree of annoyance secondary to the tinnitus will also be scored on an eleven point scale with a value of zero indicating that it is not bothersome and a value of 10 indicating that it is unbearable. Repeated measures analysis of variance (ANOVA) will be utilized to determine significance.

The 95% confidence intervals will be estimated for all D-methionine vs. placebo differences.

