13.0 STUDY TIMELINE

Up to 16 Drill Sergeant School (DSS) classes are scheduled each year and each class includes approximately 100 candidates. To meet the enrollment goal of 600 subjects it is anticipated that approximately 50 subjects per class will enroll. An estimated 504 subjects are needed to complete all follow-up assessments (252 subjects per group) to detect significant differences for the primary outcome measures. The five year proposed timeline is provided in the table below. Recruitment will begin by the fourth quarter of Year 3. New DSS Training Sessions begin approximately every two-three weeks. Approximately 50 subjects are expected to enroll per session X 13 sessions. Please note that that the protocol includes enrolling the first group and completing all procedures and data collection on that group prior to additional treatment groups. The study team will then review that process before proceeding to the next group. After all procedures are documented to be flowing smoothly recruitment will proceed from each group of DSS students with classes starting every 2-3 weeks and thus, recruitment and data collection will overlap.

| | Mar 1 2011 | | | | Mar 1 2012 | | | | Mar 1 2013 | | | | Mar 1 2014 | | | | Mar 1 2015* | | | |
|------------------------------|------------|---|---|---|------------|----|----|----|------------|----|----|----|------------|----|----|----|-------------|----|----|----|
| Years | 1 | | | | 2 | | | | 3 | | | | 4 | | | | 5 | | | |
| Months | 1 | 3 | 6 | 9 | 12 | 15 | 18 | 21 | 24 | 27 | 30 | 33 | 36 | 39 | 42 | 45 | 48 | 51 | 54 | 57 |
| Site Visit | x | | x | | | x | | | x | | | | | | | | | | | |
| Study Team Meetings | x | | x | x | x | x | x | x | x | x | x | x | x | x | x | x | x | | | |
| Prepare and File IND | x | | x | x | x | x | x | | | | | | | | | | | | | |
| IRB Submission/ Approval | | | | | | x | x | x | x | x | | | | | | | | | | |
| Order Study Drug | x | | | | | | | | | | | | | | | | | | | |
| Formulate Study Drug | x | | | | | | | | | | | | | | | | | | | |
| Finalize Recruitment Plan | | | | | | | | | | | | | | | | | | | | |
| Hire Study Staff | x | | | | | | | | x | x | x | | | | | | | | | |
| Site Training | | | | | | | | | | x | x | x | | | | | | | | |
| Finalize MOP | | | | | | | | | x | x | x | | | | | | | | | |
| Pilot | | | | | | | | | | | x | x | | | | | | | | |
| Recruit/Enroll Subjects | | | | | | | | | | | | x | x | x | x | x | x | x | | |

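### 600 enrolled with 20% attrition leaves 480 completers, not the 504 that sections 10.1 and 13.0 require; the slip costs about 2 points of power

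*Combined protocol and SAP*

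**What the plan says.** Section 10.1 assumes a placebo STS rate of about 38%, alpha of 0.05, 80% power and 1:1 allocation. It says that "a detectable difference in threshold shift rates of 30% yields a required sample size of 252 subjects for each of the two arms". It goes on: "Thus a total of 504 subjects need to complete the study". The enrolment figure follows at once: "Assuming an attrition rate of 20% in each arm over the course of the study, a total of 600 subjects will need to be enrolled".

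Section 13.0 gives the enrolment goal as 600 and repeats the requirement: "An estimated 504 subjects are needed to complete all follow-up assessments (252 subjects per group"). It also forecasts recruitment: "Approximately 50 subjects are expected to enroll per session X 13 sessions". Section 4.3 sets 300 subjects per arm.

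Three other places bear on the number analysed:

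- Section 4.8 says of subjects who have received any study treatment and "must discontinue treatment for any reason, they will not be replaced".
- Section 9.2 allows subjects with an abnormal final tympanogram to be excluded from the final analysis.
- Section 10.3 adjusts the sample size at an interim look according to the placebo shift rate.

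For the STS comparison, section 10.2 says that Fisher's "exact test will be utilized to determine statistical significance". It does not say whether the test is one- or two-sided. It adds: "The 95% confidence intervals will be estimated for all D-methionine vs. placebo differences".

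**The concern.** The three figures in section 10.1 (504 completers, 20% attrition, 600 enrolled) cannot all hold. A reader is told that enrolling 600 secures 504 completers and hence 80% power. By the plan's own attrition rate it does not.

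The STS rate is the only endpoint for which a sample size is derived, so this paragraph is what a reader will use to judge a null result. If the stated power is higher than the enrolment can deliver, a null result looks more informative than it is. The inputs behind 252 also matter because the interim re-sizing in section 10.3 checks and reuses the same assumptions.

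**Working it through.** **Attrition step.** Inputs, all from section 10.1: 252 completers per arm, 20% attrition in each arm, 600 enrolled.

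- Completers required: 2 x 252 = 504. This reproduces the plan's figure.
- Enrolment needed = completers / (1 - attrition) = 504 / 0.80 = 630 (315 per arm). The stated 600 is not reproduced.
- Completers from 600: 600 x 0.80 = 480 (240 per arm). Shortfall: 504 - 480 = 24, or 12 per arm.
- Attrition at which 600 leaves 504: 1 - 504/600 = 16%.
- A possible origin is multiplying instead of dividing: 504 x 1.20 = 604.8, rounded to 600. This is an inference.
- Forecast in section 13.0: 50 x 13 = 650 enrolled, and 650 x 0.80 = 520 completers.

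**Can 252 be reproduced?** With p1 = 0.38, d = p1 - p2, and p the mean of the two rates, the uncorrected size per arm for a two-sided 0.05 test with 80% power is

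n = [1.960 x sqrt(2p(1 - p)) + 0.842 x sqrt(p1(1 - p1) + p2(1 - p2))]^2 / d^2,

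and with continuity correction it is (n/4) x [1 + sqrt(1 + 4/(nd))]^2.

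- 30% relative: p2 = 0.38 x 0.70 = 0.266, d = 0.114, p = 0.323. n = (1.296 + 0.552)^2 / 0.114^2 = 262.9, so 263; corrected 280.2, so 281.
- 30 points absolute: p2 = 0.08, d = 0.30, p = 0.23. n = 29.7, so 30; corrected 36.04, so 37.
- One-sided at 0.05: 208 or 225 (relative), 24 or 30 (absolute).

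None of these gives 252. Two unstated treated rates come close: 26% with continuity correction (252.4) and 26.4% without it (253.5). The documents do not say which input was used, if either.

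**Power of the planned test.** These are two-sided Fisher's exact powers at alpha 0.05, from full enumeration of both binomial distributions with a placebo rate of 38%. The treated rates are assumptions.

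| D-methionine rate | 252 per arm | 240 per arm | Loss |
|---|---|---|---|
| 26.6% | 75.7% | 73.4% | 2.3 points |
| 26.4% | 77.2% | 75.0% | 2.2 points |
| 26% | 80.2% | 78.1% | 2.1 points |
| 25.7% | 82.2% | 80.3% | 1.9 points |

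The loss from 252 to 240 per arm is about 2 points whichever rate is taken. For 26.6%, Fisher power is already 75.7% with all 252 completers per arm, so most of that row's gap below 80% has nothing to do with attrition.

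**The case against.** The strongest reply is that the effect is small and that 600 is not final. Several parts of it have force.

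- The forecast of 650 in section 13.0 would leave 520 completers, which is enough. But it is a recruitment projection, and the same section states the goal as 600.
- Section 10.3 may change the sample size. Its trigger is the placebo shift rate, so it does not correct the attrition step.
- Section 4.8 bars replacement only after a subject has received some treatment. A loss between randomization and first dose could perhaps be replaced, so 480 is not a strict ceiling. Nor is it a floor for the analysis: section 9.2 can remove further subjects, and the plan does not say whether the 20% covers them.

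A reader might infer that the attrition error takes the trial from 80% power down to 73%. The documents do not support that. The attrition part is about 2 points; the rest depends on a treated rate that the plan does not state and on the choice of Fisher's test.

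A reader might also infer that power is certainly below 80%, or that 252 is a proven error. Neither is established. At 240 per arm, the uncorrected chi-square approximation gives 80.7% for 38% vs 26%. Section 10.2 words the STS aim directionally, and a one-sided Fisher test at 0.05 would give 82.8% (26.6%) or 86.3% (26%). An absolute 30-point difference would give power above 99%. The one-sided and absolute readings do not produce 252 from the stated inputs, and the 95% level and 95% intervals point to a two-sided test, so two-sided is the better inference. It remains an inference. A rounded or unstated input may well explain 252.

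**Conclusion.** The inconsistency is certain and needs no assumption: at the plan's own 20% attrition, 600 enrolled leaves 480 completers (240 per arm), 24 short of the 504 to which sections 10.1 and 13.0 tie the 80% power. Those sections are wrong as written and should be corrected.

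The consequence is modest, about 2 points of power. That figure assumes a 38% placebo rate, a treated rate near 26%, a two-sided Fisher's exact test at 0.05, and exactly 20% loss with no further exclusions. How far actual power lies from 80% cannot be settled from the documents, because the treated rate, the formula and the sidedness behind 252 are missing. That is a request for clarification and separate from the attrition slip.

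**What to change.** With no change to enrolment:

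1. Restate sections 10.1 and 13.0 to say that 600 are enrolled and that 20% attrition leaves 480 completers (240 per arm), before any exclusion for an abnormal final tympanogram under section 9.2. Call them completers, not evaluable subjects, unless the 20% is defined to cover the section 9.2 exclusions.
2. State the D-methionine STS rate in place of the bare 30% difference, and give the formula and sidedness behind 252. Only the sponsor can supply these, so this comes before step 3.
3. Replace the 80% claim with the power of the planned Fisher's exact test at 240 per arm for the stated rate. If two-sided, this is about 73% for 26.6%, 75% for 26.4% and 78% for 26%; it reaches 80% only at about 25.7% or lower.

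The cost is wording and a slightly lower stated power. If the sponsor would rather keep 504 completers, the matching enrolment at 20% loss is 630. That is 30 more subjects and within the 650 forecast in section 13.0, but the figure of 600 would then also have to change in the synopsis and in sections 1.3, 4.1, 4.3 and 11.1. Lowering the attrition assumption to 16% to make the figures agree would need supporting data.

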10.2 Primary Efficacy Analysis

Two groups are planned in the randomized prospective design: the D-met and the placebo groups. The primary objectives, and their associated analyses, for this study are as follows:

1. To determine if there is a significant difference between the D-methionine and placebo treated groups in the average severity of documented side effects where severity is defined as the frequency of side effect multiplied by the intensity of the side effect. Repeated measures analysis of variance (ANOVA) will be utilized to determine significance.
2. To determine if there is a significantly reduced change in threshold hearing in each ear, adjusting for handedness, for the D-methionine group as compared to the placebo group at the tested audiometric frequencies. The tested audiometric frequencies will be 0.5, 1, 2, 3, 4, 6 and 8 kHz. Multi-way (2 groups x 7 frequencies) analysis of variance (ANOVA) with interaction effects and correction for multiple comparisons (Newman-Keuls) will be utilized to determine significance. Determination for early detection will be according to the American Speech-Language Hearing Association (ASHA, 1994) criteria of: 1) greater than or equal to a 20 dB change at any frequency, 2) greater than or equal to a 10 dB change at any 2 adjacent frequencies, or 3) loss of response at 3 consecutive frequencies where responses were obtained at baseline. To be considered significant ototoxicity, these changes must replicate within 24 hours (may be immediate) with no indication of middle ear abnormality. Subjects serve as their own controls for audiometric change, which is computed relative to baseline measures.
3. To determine if there is a significantly lower rate of STS (in either ear) for the D-methionine group as compared to the placebo group where STS is defined according to DOEHRSHC criteria as an increase of 10 dB or greater change (decrease in hearing) for the average of 2, 3 AND 4 kHz in

either ear. A significant negative STS (improved hearing) is defined as a decrease of 10 dB or greater change for the average of 2, 3 AND 4 kHz in either ear. An early warning shift STS (decrease in hearing) is defined as a 15 dB or greater change at 1, 2, 3 OR 4 kHz in either ear. Fisher's exact test will be utilized to determine statistical significance.

Secondary objective of the study is as follows:

1. To determine if there is a significant difference in reported level of tinnitus between the D-methionine and the placebo groups where the level (loudness) of tinnitus will be scored on an eleven point scale with a value of 0 associated with very quiet and a value of 10 associated with very loud and on an eleven point scale where the degree of annoyance secondary to the tinnitus will also be scored on an eleven point scale with a value of zero indicating that it is not bothersome and a value of 10 indicating that it is unbearable. Repeated measures analysis of variance (ANOVA) will be utilized to determine significance.

The 95% confidence intervals will be estimated for all D-methionine vs. placebo differences.

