| TREATMENTS | 
Two doses per day of an orange-flavored oral suspension (D-methionine or placebo) starting 3 days prior to weapons training, 11 days during weapons training, and 4 days after completion of weapons training. The total daily dose of D-methionine is up to 100 mg/kg fractionated into 2 doses of 50 mg/kg each.
 |
| MAIN PARAMETERS OF EFFICACY | 
Primary endpoint is to confirm safety and tolerability of up to 100 mg/kg daily given in divided doses approximately 12 hours apart.
 
Primary efficacy endpoint is change from baseline in pure-tone threshold as measured by absolute change and frequency of significant noise-induced threshold shift (STS).
 
Secondary efficacy endpoint is change from baseline scores for the tinnitus scales for both loudness and annoyance.
 |
| MAIN PARAMETERS OF SAFETY | 
Adverse event assessments will be made by study coordinator(s) as study drug is dispensed (twice daily) and at the end of the study.
 
Adverse events will be summarized by treatment group according to the last treatment taken before the Adverse Event (AE) began.
 |
| STOPPING RULES | 
Adverse event resulting in death, emergency surgery, or permanent and irreversible disability, unless determined unrelated to study participation. If an unexpected adverse event occurs in more than 3 subjects, then the risk of the active drug will be compared against risk of the placebo. Significantly higher rates in the active study group, based on severity of the adverse event, could warrant stopping trial.
 |
| DATA MONITORING | 
An on-site research monitor and an off-site medical monitor are assigned to this protocol. The project director, principal investigator, medical monitors, coordinator(s) and data manager of this protocol will schedule regular meetings via video or telephone conference to review study progress and safety data. The regulatory representative will also attend as needed, via teleconference, to determine if there are regulatory concerns or issues to handle based on the meeting content and outcome.
 |

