| STATISTICAL ANALYSIS | 
To confirm that the total daily dose of D-methionine 100mg/kg fractionated into 2 doses of 50 mg/kg each is safe and tolerable.
 
To determine if there is significantly reduced change in threshold hearing in each ear, adjusting for handedness, for the D-methionine group as compared to the placebo group at the tested audiometric frequencies.
 
To determine if there is a significantly lower rate of STS (in either ear) for the D-methionine group compared to the placebo group.
 
To determine if there is a significant difference in reported level of tinnitus between the D-methionine and the placebo groups.
 |

Clinical Trial Schema

List of Abbreviations

| | |
|----------|---|
| AAA | American Academy of Audiology |
| ACE-Mg | ACE-Magnesium |
| ADR | Adverse Drug Reaction |
| AE | Adverse Event/Adverse Experience |
| ANSI | American National Standards Institute |
| CCR | Center for Clinical Research |
| CFR | Code of Federal Regulations |
| COI | Conflict of Interest |
| CONSORT | Consolidated Standards of Reporting Trials |
| CRF | Case Report Form |
| DDEAMC | Dwight D. Eisenhower Army Medical Center |
| D-met | D-methionine |
| DFMO | Difluoromethylornithine |
| DHHS | Department of Health and Human Services |
| DOEHRSHC | Defense Occupational Environmental Health Readiness System-Hearing Conservation |
| DSM | Data and Safety Monitoring |
| FDA | Food and Drug Administration |
| FWA | Federal Wide Assurance |
| GCP | Good Clinical Practice |
| GSH | Glutathione |
| GSSG | Oxidized Glutathione |
| HIPAA | Health Insurance Portability and Accountability Act |
| IB | Investigator's Brochure |
| ICF | Informed Consent Form |
| IDE | Investigational Device Exemption |
| IND | Investigational New Drug |
| IRB | Institutional Review Board |
| ISM | Independent Safety Monitor |
| JC | Joint Commission |
| MACH | Moncrief Army Community Hospital |
| MCRD | Marine Corps Recruit Depot |
| N | Number (typically refers to participants) |
| NAC | N-acetylcysteine |
| NB | Narrow Band |
| NIHL | Noise Induced Hearing Loss |
| NCI | National Cancer Institute, NIH |
| NIH | National Institutes of Health |
| PI | Principal Investigator |
| PK | Pharmacokinetics |
| PTA | Pure Tone Average |
| QA | Quality Assurance |
| QC | Quality Control |
| SAE | Serious Adverse Event |
| SOP | Site Operations Manual |
| STS | Significant Noise-Induced Threshold Shifts |
| WHO | World Health Organization |

Definitions

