1.0 OBJECTIVES

1.1 Primary Objectives

1.1.1 To monitor for any potential side effects of D-methionine in human subjects. This aim will be accomplished by assessing for side effects each time study drug is dispensed (twice daily by the study coordinator(s) and at the final study visit.

1.1.2 To determine whether administering oral D-methionine can prevent permanent noise-induced hearing loss (NIHL) due to impulse noise associated with required M-16 weapons training. This aim will be addressed by comparing the results of D-methionine versus placebo administration starting 3 days prior to, during the 11 day period of weapons training (Monday-Friday and Monday -Thursday over a 2 week period), and 4 days after weapons training for a total of 18 days of dosing. Pure tone air conduction hearing thresholds will be assessed before and 15-16 days after completion of weapons training (i.e., 11-15 days after the last day of study drug/placebo administration).

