4.2 Study Endpoints

4.2.1 Primary Endpoints

- The first primary endpoint is to confirm safety and tolerability of administering up to 100 mg/kg daily, given in divided doses, twice daily (with morning and evening meal). The other primary efficacy endpoint is change from baseline in pure-tone thresholds as measured by absolute change and frequency of significant noise-induced threshold shift (STS).

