4.7 Subject Withdrawals

Every effort will be made to ensure that subjects complete the study through the 30 day study period, consistent with provisions of informed consent and good clinical judgment with respect to safety. The following are potential reasons to terminate the participation of a subject in the study:

1. The subject's health would be jeopardized.
2. Lost to follow-up: the subject fails to return to the site for scheduled visits and does not respond to reminders or attempts to contact.

3. Withdrawal of consent: subject decides to stop participation for any reason or is unable to complete the study as described in the protocol. The investigator will make a reasonable effort by person-to-person or telephone interview if allowed by the withdrawn volunteer, to ascertain the subject's reason(s) for withdrawal.

The reason for withdrawal will be captured on the appropriate case report form (CRF) and the medical monitor will be informed of removal or early withdrawal of a subject from the study.

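### The primary safety test is an ANOVA on a frequency-times-intensity score with no unit for frequency, and no criterion lets it confirm safety

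*Combined protocol and SAP*

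**What the plan says.** Safety is the first of the primary aims. Section 4.2.1 states: "The first primary endpoint is to confirm safety and tolerability of administering up to 100 mg/kg daily". The synopsis has "Primary endpoint is to confirm safety and tolerability of up to 100 mg/kg daily" and, under Statistical Analysis, "To confirm that the total daily dose of D-methionine 100mg/kg fractionated into 2 doses of 50 mg/kg each is safe and tolerable". Section 1.1.1 is milder: "To monitor for any potential side effects of D-methionine in human subjects". Section 8.1 speaks of evaluating treatment-emergent adverse events and changes in concomitant medication.

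The analysis is in section 10.2, objective 1. It looks for a significant difference between arms "in the average severity of documented side effects". The test is a repeated-measures ANOVA, and the score it uses is a product: "severity is defined as the frequency of side effect multiplied by the intensity of the side effect".

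The other relevant provisions are these:

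- Section 8.4.1 has subjects questioned before every dose and on the last study day. For each event it records onset, duration, intensity and relationship to study drug. Events are graded on a Grade 1 to 5 table.
- Section 8.4.1 compares side effects between arms at baseline, during treatment and after treatment. Frequency is among the features compared, but it is not defined.
- Section 8.4.1 tabulates adverse events by severity and body system in everyone who took at least one dose. The synopsis adds "Adverse events will be summarized by treatment group".
- Section 8.7 gives stopping rules and section 8.8 gives committee review. Section 10.2 closes by promising 95% confidence intervals for all differences between arms.

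**The concern.** There are two linked problems.

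First, the score cannot be computed from the plan. Frequency could be the number of events, days, or dose contacts at which the symptom is reported, and section 8.4.1 collects no frequency item, so it must be derived. How several side effects in one subject combine is not stated. Nor is which ANOVA effect decides: group, or group by time. Because the score is a product, duration under one counting rule trades against grade. The rule can therefore settle whether the primary safety test is significant and, in some settings, which arm looks worse.

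Second, the stated aim is to confirm safety, while the test is one of difference. Without a margin or an upper bound, a non-significant result shows only that no difference was detected. A significant result gives a mean score difference with no clinical unit. In neither case does the reader learn what excess risk the trial has excluded.

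**Working it through.** The plan gives no sample size, power or threshold for safety, so there is no stated figure to reproduce. Section 10.1 sizes the trial on the threshold-shift rate alone. From the documents come 300 subjects per arm (section 4.3), two doses a day for 18 days, and Grades 1 to 5. All event rates and durations below are assumptions chosen to show dependence on the rule. They are not predictions.

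**1. Range of the score.** 18 × 2 = 36 dose contacts. Questioning precedes each dose, so the first contact comes before any drug and at most 35 dose contacts can capture an on-treatment effect. One continuous Grade 1 symptom can score 1 (one event) or as much as 35 (one report per contact).

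**2. Mild against severe.** Take Grade 1 nausea at both daily contacts for 6 days, and Grade 3 vomiting at one contact.

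| Counting rule | Mild nausea | Severe vomiting |
|---|---|---|
| Contacts | 12 × 1 = 12 | 1 × 3 = 3 |
| Days | 6 × 1 = 6 | 1 × 3 = 3 |
| Episodes | 1 × 1 = 1 | 1 × 3 = 3 |

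The ranking reverses. Suppose such mild nausea occurs in 5% on D-methionine and 10% on placebo, and such severe vomiting in 8% and 2%. The mean scores (D-methionine, placebo) are:

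- Contacts: 12 × 0.05 + 3 × 0.08 = 0.84, against 12 × 0.10 + 3 × 0.02 = 1.26.
- Episodes: 0.05 + 0.24 = 0.29, against 0.10 + 0.06 = 0.16.

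The arm with four times the severe vomiting looks better under one rule and worse under the other.

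**3. Effect on significance.** Assume one Grade 1 symptom in 30% on D-methionine and 20% on placebo, with geometric duration of mean 6 contacts in both arms. Event-free subjects score zero. The group effect of a balanced repeated-measures ANOVA is a two-sample test on subject totals.

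- Counted once: difference 0.10, variances 0.21 and 0.16, so z = 0.10 / √(0.37/300) = 2.85. The chance of a significant excess is about Φ(2.85 − 1.96) = 81%.
- Counted per contact: a geometric variable with mean 6 has mean square 66. The variances are 0.3 × 66 − 1.8² = 16.56 and 0.2 × 66 − 1.2² = 11.76. The difference is 1.8 − 1.2 = 0.60, so z = 0.60 / √(28.32/300) = 1.95 and the chance is about 50%.

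Simulation of 20,000 trials, with durations capped at 36, gives 81% and about 50 to 51%. With mean durations of 2 or 12 contacts, counting once still gives 81%; per-contact counting gives about 60% and 52 to 53%.

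**4. Effect on direction.** Keep the incidences, but let D-methionine symptoms last half as long (mean 3 contacts). Counted once, the means are 0.30 against 0.20. Per contact they are 0.30 × 3 = 0.90 against 0.20 × 6 = 1.20. In simulation, counting once shows a significant excess on D-methionine in 81% of trials. Per-contact counting shows D-methionine significantly better in 22% to 25% across separate runs.

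**5. The same data as proportions.** 90/300 against 60/300 is a difference of 10.0 points (Newcombe 95% interval 3.1 to 16.8), whatever the counting rule.

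**6. What non-significance would mean.** Power for a two-sided 0.05 test to detect a doubled adverse-event rate:

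| Assumed placebo rate | 252 per arm | 300 per arm |
|---|---|---|
| 1% | 15% | 17% |
| 5% | 57% | 64% |
| 10% | 88% | 93% |

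For uncommon events, a non-significant result is compatible with a doubling.

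**The case against.** The strongest reply is that much of this is already in the protocol. The intensity half of the score has a written scale in section 8.4.1; only a cross-reference is missing. That section also names likely comparison periods and sets a dosed-subject denominator for the adverse-event table. Recording each event once, with a duration, favours counting events, so one report per contact is the extreme reading. Tabulation by severity, confidence intervals and the rate comparison in stopping rule 3 do not depend on the score. Sections 1.1.1 and 8.1 already use softer words than *confirm*. All of this stands, and it narrows the point to two gaps: no unit for frequency, and no criterion for *confirm*. A confidence interval on an undefined score inherits the ambiguity, and stopping rule 3 leads to a committee decision on stopping, not to a finding of safety.

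It is also fair that the rates above are invented. Section 2.6 reports no side effects in excess of placebo in earlier studies, and the reversal in step 4 needs a difference in duration that nothing in the documents predicts.

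Three stronger readings are tempting but not supported:

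- A reader might infer that severe harm could pass unnoticed. Events above Grade 2 are handled as serious, and sections 8.7 and 8.8 apply regardless of the score.
- A reader might infer from "in the average severity of documented side effects" that the average covers only subjects with events, so that an excess in incidence disappears. The wording permits this, but the adverse-event table uses all dosed subjects. A low detection rate under that reading with equal durations would also prove nothing, because the mean per event is then equal in both arms by construction.
- A reader might infer that the scoring rule will be chosen after unblinding. The case report forms, manual of procedures and data-handling procedures are separate documents and may contain recording rules. What can be said is that the analysis rule is not in this plan.

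**Conclusion.** The point holds, and it is more than missing detail. Followed as written, the plan could let a non-significant p-value on an undefined score stand as confirmation of safety. The absence of a frequency unit and of a criterion for *confirm* can be read directly from the text and needs no assumption. The size of the effect does rest on assumptions: about 80% against 50% for a significant excess under two reasonable counting rules, and a possible change of direction if durations differ between arms. These figures show sensitivity to the rule, not the likely result. The efficacy conclusions and ongoing safety oversight are not affected.

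**What to change.** In all subjects receiving at least one dose, make the primary safety analysis the subject-level proportion in each treatment arm with:

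- any adverse event;
- any event of Grade 2 or higher;
- any event of Grade 3 or higher.

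Show serious adverse events separately, by the outcome definition in section 8.3, because section 8.4.1 also treats everything above Grade 2 as serious and the two definitions differ. For each measure give the D-methionine minus placebo risk difference with its 95% confidence interval, and state the excess risk that the upper limit excludes. Report withdrawals for an adverse event only where the reason recorded under section 4.7 identifies one; that section has no such category.

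Keep the product score as descriptive only, with its frequency unit defined and the section 8.4.1 grades cited.

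Reword *confirm* in the synopsis and section 4.2.1 as *evaluate*, in line with sections 1.1.1 and 8.1. If *confirm* is kept, name one measure and the excess to be excluded before unblinding. In either case, do not infer safety from a non-significant p-value.

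The cost is wording and one table, from data already collected. The score loses its primary role. The intervals will be wide: with 300 per arm and equal rates, about ±2.5 points at 2%, ±4.9 at 10% and ±6.4 at 20%. No general gain in power is claimed.
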